## 2. INTRODUCTION

This statistical analysis plan (SAP) provides the detailed methodology for summary and statistical analyses of the data collected in Study B5381012. This document may modify the plans outlined in the protocol; however, any major modifications of the primary endpoint definition or its analysis will also be reflected in a protocol amendment.

### 2.1. Study Objectives, Endpoints, and Estimands

The primary objective of the study is to evaluate interchangeability of PF-06410293 and Humira by examining adalimumab steady-state pharmacokinetics (PK) in a switching arm (following 3 switches between Humira and PF-06410293) as compared to a non-switching arm (receiving only Humira). The secondary objectives are

- To evaluate other serum adalimumab PK parameters in the switching arm and the non-switching arm.
- To evaluate the overall safety and tolerability of the switching arm and the non-switching arm.
- To evaluate immunogenicity of the switching arm and the non-switching arm.

#### 2.1.1. Primary Estimand(s)

The primary estimand of this study is defined according to the primary objective and is in alignment with the primary endpoint. The primary estimands are the geometric mean ratio (GMR) and 90% confidence interval (CI) for  $AUC_{\tau}$  and  $C_{max}$  to evaluate the PK equivalence

between the switching and non-switching arms, after 3 switches, in participants with RA who meet the PK population criteria that include criteria for the number and timing of missing doses, availability of PK sample data, adherence to background therapy, and major protocol deviations related to PK assessment (Section 4).

### 2.1.2. Secondary Estimand(s)

The secondary estimands are

- Other serum adalimumab PK parameters, including time at which  $C_{\max}$  occurs ( $T_{\max}$ ), average concentration over the dosing interval ( $C_{\text{av}}$ ), and apparent clearance ( $CL/F$ ) obtained during the intensive PK sampling interval in participants who meet the PK population criteria. Pre-dose concentrations during multiple dosing ( $C_{\text{trough}}$ ) obtained at scheduled PK sample timepoints will also be assessed in participants who meet the safety population criteria, for the switching arm and non-switching arm.
- Safety endpoints for the switching arm and non-switching arm in participants who meet the safety population criteria.
- Summarize percent of participants with antidrug antibodies (ADA), and neutralizing antibodies (NAb) and ADA/NAb titers over time for the switching arm and non-switching arm in participants who meet the Safety population criteria.

## 2.2. Study Design

[figure not shown]
This is an open-label, multi-national, 2-arm, randomized, parallel-group study designed to evaluate the interchangeability of the switching arm (PF-06410293 and Humira), compared to non-switching arm (Humira), in participants with moderately to severely active RA on background methotrexate (MTX). For purposes of this protocol, the treatment arm that includes switches between PF-06410293 and Humira will be referred to as the “switching” arm, while the treatment arm that comprises continuous Humira treatment will be referred to as the “non-switching” arm.

This study will enroll a maximum of approximately 420 participants so that approximately 314 evaluable participants complete the study.

Study treatment will be provided through 4 treatment periods. For the first 10 weeks, all participants will receive Humira [Treatment Period (TP) 1]. Upon completion of TP1, participants will be randomized (1:1 ratio) into either the switching or non-switching arm prior to dosing on Week 10. Randomization will be stratified by 3 body weight groups (Week 10 weight) ( $\geq 40$  kg to  $< 70$  kg;  $\geq 70$  kg to  $< 100$  kg;  $\geq 100$  kg to  $\leq 130$  kg). Participants randomized to the non-switching arm will continue on Humira for the remainder of the study, and participants randomized to the switching arm will continue switching in each TP (TP2: PF-06410293; TP3: Humira; TP4: PF-06410293).

- Treatment Period 1 (Lead In Period) will begin with the first dose of investigational product on Week 0 (Day 1) and conclude with the completion of Week 10 pre-dose assessments.
- Treatment Period 2 will begin with the 1:1 randomization of the participants to either the switching arm or the non-switching arm at Week 10. Investigational product dosing for Week 10 will begin after the randomization process in the respective treatment arms and will conclude with the completion of Week 16 pre-dose assessments.
- Treatment Period 3 will begin with investigational product dosing on Week 16, and conclude with the completion of Week 22 pre-dose assessments.
- Treatment Period 4 will begin with investigational product dosing on Week 22 and continue through Week 30, where onsite investigational product dosing is scheduled at Weeks 22, 24, 26, 28, and 30, followed by a 2-week PK sampling period from Week 30 to Week 32. TP4 will conclude with end of treatment (EoT) assessments and final dose administration at Week 32.
  - The 2-week PK sampling period within TP4 starts with Week 30 predose PK collection and ends with predose PK collection on Week 32.
- Safety Follow-Up Period begins after the last investigational product dosing on Week 32, and concludes at completion of the Week 36 assessments. All participants (including early discontinuations) will be followed for at least 28 calendar days from the date of their last dosed investigational product. Week 36 safety follow up may be conducted via phone.

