#### 9.2. Sample Size Determination

Assuming a GMR (switching arm vs non-switching arm) of 105% and a coefficient of variation (CV) of 55% for each of the PK parameters,  $AUC_{\tau}$  and  $C_{max}$ , an anticipated non-evaluable rate of 25%, and a correlation of 0.5 between log-transformed  $AUC_{\tau}$  and log transformed  $C_{max}$ , a total sample size of approximately 420 participants (314 evaluable participants) would provide 85% power to demonstrate that the 90% CI for the GMR is within 80.00% to 125.00% for both parameters.

The %CV assumption for the power calculation was derived from data on 15 RA participants receiving MTX who participated in a PK substudy of an innovator study, with %CV of 53% and 56% for  $AUC_{\tau}$  and  $C_{max}$ , respectively, and from 21 RA participants (6 on MTX) who participated in a PK substudy of the innovator open-label extension study, where %CV

for all participants was 48% and 49%, and for MTX only was 46% and 44%, for  $AUC_{\tau}$  and  $C_{max}$ , respectively.

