### **10.11. Appendix 11: COVID-19 Pandemic Considerations**

In response to the ongoing global pandemic COVID-19, and the increasing restrictions and concerns on public health, the following changes are being incorporated into the B5381012 protocol to clarify alternative solutions to accommodate study procedures during the unprecedented time (eg the COVID-19 pandemic).

The following alternative solutions are only acceptable during the COVID-19 pandemic:

- The PI should document the start and end date of the necessity to use alternative solutions as described herein. Local law and regulations may apply.
- For participants who have received study treatment, scheduled study visits may be done remotely.
- For study drug dispensation, study drugs may be dispensed via a courier arranged by the investigational site, the home health care service or alternative transports as agreed upon between site and study participant. Please be sure alternative drug dispensation is in accordance with applicable laws and regulations.
- A home health care service will be added as an option to scheduled study visits after the Day 1/Week 0 Visit to: provide investigational product to study participants, including administration of study treatment, collect vital signs and specimens and/or processing of laboratory tests as specified in the protocol. In these cases, the investigator or designee must contact the study participants to collect adverse event (AE)/serious adverse event (SAE) information. Investigator or designee should also confirm dosing data with the participant and record it in the site's source or eDiary.
- Randomization at Week 10 may be done off-site:
  - Body weight is required to be taken at Day 1 or at Screening, whichever is closer to the Week 10 visit, and will be used to randomize as stated in the protocol.
  - Sites will need to call IWRS to randomize the study participant into either the switching arm (PF-06410293) or non-switching arm (Humira) for treatment. Once treatment assignment is received, site may dispense the study medication and deliver it to the participant as described below.
  - The home health care service may be used to collect specimens for safety evaluation, PK, ADA/NAb, vital signs and possibly deliver study medication.
- Dosing compliance confirmation should be recorded by study site investigator(s)/staff remotely in site's source documents or in eDiary at the time of the remote visit. Dosing data must be entered timely in the eCRF.

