## 5. GENERAL METHODOLOGY AND CONVENTIONS

### 5.1. Hypotheses and Decision Rules

null hypothesis:  $H01 \quad \frac{\mu_s}{\mu_{ns}} < 0.8$                       or  $H02 \quad \frac{\mu_s}{\mu_{ns}} > 1.25$

alternative hypothesis:  $H_a \quad 0.8 \leq \frac{\mu_s}{\mu_{ns}} \leq 1.25$

$\mu_s$ : geometric mean for the switching arm

$\mu_{ns}$ : geometric mean for the non- switching arm

Interchangeability will be established statistically if the 90% CI for the GMR is within 80.00% to 125.00% for both  $C_{max}$  and  $AUC_{\tau}$ .

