#### 5.2.1. Analyses of Variance (ANOVA)

ANOVA will be used for comparing switching arm vs non-switching arm for  $C_{max}$  and  $AUC_{\tau}$ . GMR and the associated 90% 2-sided CI are will be obtained using analysis of ANOVA applied to log-transformed data, with terms for treatment and randomization stratification factor (body weight categories).

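### Optional precision gain: the primary ANOVA uses body weight only as three bands, and adding continuous log weight would raise joint power by about 0.3 to 1.7 points under stated assumptions

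*SAP*

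**What the plan says.** SAP 2.2 (and Protocol 4.1 and 6.3) sets the strata: "Randomization will be stratified by 3 body weight groups (Week 10 weight", namely 40 to below 70 kg, 70 to below 100 kg, and 100 to 130 kg inclusive. SAP 5.2.1 fits the primary ANOVA to log-transformed data "with terms for treatment and randomization stratification factor (body weight categories". SAP 6.1.1 and Protocol 1.1 and 9.4.3.1 give the same model, and none of them has a continuous weight term.

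The Schedule of Activities in Protocol 1.3 measures body weight at Screening, Baseline, Week 10 and Week 32, so at least one pre-randomisation weight is planned for every participant. If the Week 10 weight is missing, footnote 10 of that schedule allows the Screening or Baseline weight nearest to Week 10. For off-site randomisation in the pandemic, Protocol Appendix 11 says: "Body weight is required to be taken at Day 1 or at Screening, whichever is closer to the Week 10 visit".

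On the decision rule, SAP 5.1 states: "Interchangeability will be established statistically if the 90% CI for the GMR is within 80.00% to 125.00% for both" primary endpoints. Protocol 9.2 gives the power basis: "Assuming a GMR (switching arm vs non-switching arm) of 105% and a coefficient of variation (CV) of 55% for each of the PK parameters", with "an anticipated non-evaluable rate of 25%, and a correlation of 0.5" between the two log-transformed endpoints. It concludes that "a total sample size of approximately 420 participants (314 evaluable participants) would provide 85% power".

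**The concern.** Any relation between weight and adalimumab exposure inside a 30-kg band stays in the residual of the planned model. A larger residual widens both 90% confidence intervals, and both must fall within the margins. The weights that would remove part of that residual are already in the database, taken before the first randomised dose. What is at stake is a little precision on each primary endpoint. The validity of the test is not in question.

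**Working it through.** **Inputs from the documents.** GMR 1.05, CV 55%, correlation 0.5, 314 evaluable, 25% non-evaluable (Protocol 9.2); 1:1 allocation (SAP 2.2); 90% CI within 80.00-125.00% on both endpoints (SAP 5.1).

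**Assumptions not in the documents.** Weight log-normal, truncated to 40-130 kg, with mean/SD of 72/15, 76/18 or 82/20 kg. Slope of log exposure on log weight from -0.5 to -1.0.

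**1. The plan's own figure.**
- Log-scale SD = sqrt(ln(1 + 0.55²)) = 0.514; variance 0.2643.
- SE of the log GMR = 0.514 × sqrt(4/314) = 0.0580.
- Half-width of the 90% CI = 1.650 × 0.0580 = 0.0957.
- The log GMR estimate must lie within ±(0.2231 - 0.0957) = ±0.1274. With true value ln 1.05 = 0.0488, single-endpoint power is Φ((0.1274 - 0.0488)/0.0580) less a lower-tail term of about 0.001, which is 91.1%.
- Joint power for two endpoints correlated at 0.5, by simulation: 84.9%, against the stated 85%.
- 314/(1 - 0.25) = 419, against the stated 420 or so.

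The plan reproduces without relying on any covariate gain.

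**2. What the bands leave out.** The within-band share is the variance of log weight inside bands divided by its total variance.

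| Mean/SD (kg) | Variance of log weight | Within bands | Share left |
|---|---|---|---|
| 72/15 | 0.0408 | 0.0110 | 0.27 |
| 76/18 | 0.0498 | 0.0113 | 0.23 |
| 82/20 | 0.0505 | 0.0102 | 0.20 |

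The bands therefore already capture 73-80% of the variance of log weight.

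**3. Gain if 55% is the residual CV of the banded model.** Cut in residual variance = slope² × within-band variance / 0.2643.
- Slope -0.5: 0.25 × 0.0102/0.2643 = 1.0% (82/20) to 0.25 × 0.0113/0.2643 = 1.1% (76/18).
- Slope -1.0: 0.0102/0.2643 = 3.9% (82/20) to 0.0113/0.2643 = 4.3% (76/18).
- Equivalent evaluable participants: 314 × 0.010 = 3 up to 314 × 0.043 = 13 or so.
- Joint power goes from 84.9% to between 85.3% and 86.6%, a gain of 0.4 to 1.7 points (0.3 at the low end if counted from the stated 85.0%).

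**4. Gain if 55% is the unadjusted CV.** The substudies cited in Protocol 9.2 mention no weight adjustment, so this reading is also open. For 76/18 and slope -1.0:
- Share of log-exposure variance due to weight: R² = 0.0498/0.2643 = 0.189.
- Residual with bands: 1 - 0.189 × 0.773 = 0.854. With continuous weight: 1 - 0.189 = 0.811.
- Ratio 0.950, a cut of 5.0%, worth about 314 × 0.050 = 16 participants.

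Power on this reading starts above 85%, because the bands themselves help. With the bands capturing 75%, it moves from 86.4% to 86.9% at R² = 0.05, and from 90.6% to 92.3% at R² = 0.20.

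**5. Sensitivity.** R² = 0.30 would lift 85.0% to 88.6% on the residual-CV reading. That needs a slope steeper than -1.0, since the largest R² in the grid above is 0.0505/0.2643 = 0.19.

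**The case against.** The strongest reply is that this is a preference. Adjusting for the randomisation stratum is valid, the protocol and SAP specify the same model, and the power claim does not depend on a better one. In an open-label trial with ongoing sponsor review of data (SAP 7.1) and a SAP already at Version 2, changing the primary covariates for about one power point could look data-driven. Protocol 9 and SAP 2 also require an amendment for a major change to the primary analysis. All of that stands. It sets the terms on which the change can be made and makes the supportive route reasonable. It does not remove the gain.

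A reader might also infer four stronger points, which the documents do not support.
- **The sponsor stratified on weight because it drives exposure.** No section gives a reason. The slope used here is an assumption.
- **Chance weight imbalance inside a band biases the GMR.** Under randomisation this is sampling variation, which the 90% CI already covers. It is the residual-variance point again.
- **The closed limits of 40 and 130 kg cost precision.** They match the entry limits in inclusion criterion 7. If weight changes over 10 weeks with an assumed SD of 2-4 kg, roughly 1-2 of 420 would fall outside. That is a wording gap.
- **The older fallback weight is an unplanned inconsistency that costs precision.** Footnote 10 of the Schedule of Activities prespecifies it, and the documents do not show how often it was used. Under the same assumed changes, about 5-10% of those stratified on an older weight would sit in a different band at Week 10. The added covariate would not help where the older weight is the only one available.

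**Conclusion.** The point holds as an optional improvement. The planned ANOVA is sound and its 85% joint power is confirmed. Banding weight leaves 20-27% of the variance of log weight unused under the assumed distributions. Recovering it cuts residual variance by about 1-5%, where the upper end applies if 55% is the unadjusted CV. If 55% is the residual CV, joint power rises by about 0.3-1.7 points. The direction follows from the model whenever exposure varies with weight inside the bands. The size rests wholly on the assumed weight distribution and slope. Nothing here suggests that the trial is underpowered or that its primary conclusion would be biased.

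**What to change.** Before database release, and without reference to PK results by arm:

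1. In SAP 5.2.1 and 6.1.1, keep the weight stratum as randomised and add the log of the last body weight measured before the first randomised dose as a continuous covariate.
2. Put matching text in Protocol 1.1 and 9.4.3.1 through an amendment, so that protocol and SAP describe one primary model.
3. If the sponsor prefers not to amend, leave the primary ANOVA as it is and prespecify the log-weight model in the SAP as a supportive analysis.
4. At most, add one sentence assigning a Week 10 weight outside 40-130 kg to the nearest band. This is a clarification with no claim to precision.

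The cost is one model degree of freedom and, for the primary-model route, an amendment to the primary-analysis text. No new data are needed. The supportive route costs SAP text only, but it serves as a robustness check and adds no power to the primary test.

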**Figure 1. Study Design**

### 3. ENDPOINTS AND BASELINE VARIABLES: DEFINITIONS AND CONVENTIONS

#### 3.1. Primary Endpoint(s)

The primary endpoints are  $C_{max}$  and  $AUC_{\tau}$  obtained during the intensive PK sampling interval.

#### 3.2. Secondary Endpoint(s)

The secondary endpoints are

- Other serum adalimumab PK parameters and serum concentration, including  $T_{max}$ ,  $C_{av}$ , and  $CL/F$  obtained during the intensive PK sampling interval and  $C_{trough}$  obtained at scheduled PK sample timepoints.
- Safety endpoints including adverse events (AEs), laboratory test and vital signs. More detailed information is provided in Section 3.5.
- ADA and NAb endpoints including percent of participants with ADA/NAb and ADA/NAb titers over time.

### 3.3. Other Endpoint(s)

Other endpoints include demographic and baseline characteristics, such as participant age, sex, height, weight, race, ethnicity, and medical history, and study drug administration.

### 3.4. Baseline Value

For the TP1 summary, the baseline value is defined as the most recent measurement prior to the first dose of investigational product in TP1. For the TP2 to TP4 summary, the baseline value is defined as the most recent measurement prior to the first dose of investigational product after randomization in TP2.

### 3.5. Safety Endpoints

#### 3.5.1. Adverse Events

A treatment-emergent adverse event (TEAE) for TP1 summary is defined as any adverse event that occurs after the beginning of the study treatment in TP1 and before the first dose of investigational product administered after randomization in TP2.

A treatment-emergent adverse event (TEAE) for TP2 to TP4 summary is defined as any adverse event that occurs after the first dose of investigational product administered after randomization in TP2. Adverse events of special interest (AESI) include Targeted medical events (TME) which are defined for Adalimumab biosimilar program and are maintained in a list in the product's Safety Review Plan.

Immunogenic adverse effects include injection-site reactions (ISRs); medically evaluated AEs that meet Sampson Criteria, and medically evaluated AEs identified by broad MedDRA SMQ for Hypersensitivity/Anaphylaxis /Angioedema; medically evaluated AEs identified as potential Cytokine storm, and medically evaluated AEs identified as potential Delayed immune responses.

#### 3.5.2. Laboratory Data

Laboratory data include hematology, chemistry, and urine routine safety laboratory tests results at each visit.

#### 3.5.3. Vital Sign Data

Vital signs endpoints include body temperature, pulse rate, respiratory rate, and blood pressure.

## 4. ANALYSIS SETS (POPULATIONS FOR ANALYSIS)

Data for all participants will be assessed to determine if participants meet the criteria for inclusion in each analysis population prior to releasing the database and classifications will be documented per standard operating procedures.

All subjects at site **CCI** will be excluded from all the analysis populations due to violation of GCP principles (i.e., suspected falsification of study records).

Population	Description
Enrolled Population	All participants who are enrolled in TP1. This population will be used for participant accountability in TP1.
Safety Population for TP1 (Safety-TP1)	All participants who are enrolled in TP1 and receive at least one dose of investigational product in TP1. This population will be used for the TP1 safety analyses.
Intent-to-Treat Population (ITT-Randomized)	All participants who are randomized to a study treatment group at Study Week 10. This population will be used for participant accountability during TP2 through TP4.
Safety Population (Safety-Randomized)	All participants who are randomized and receive at least one dose of investigational product following the randomization at Study Week 10. The Safety Population will be used for the safety analyses during TP2 and beyond, ADA and NAb analyses and the secondary PK endpoint ( $C_{\text{trough}}$ ).
PK population	All randomized participants who are dosed to initiate the Week 30 steady-state PK profile, remain on background MTX with no major protocol deviations influencing the PK assessment, such as a miss dose (the first dose of the study in TP1 cannot be missed, no more than 1 missed dose allowed per TP except Week 32 dose, no more than 2 missed doses allowed in TP1 through TP4 except Week 32 dose, participants can only miss or have an incomplete dose for either the first or second dose in TP4 (but not both), and the study doses on Weeks 26, 28, and 30 cannot be missed or incomplete), and have at least 1 primary endpoint ( $AUC_{\tau}$ or $C_{\text{max}}$ ). The last study dose in TP4 on week 32 after the PK assessments is not included in the definition of the population for analyses and can be missed or be incomplete. Subjects will be excluded from the PK population in case of missed PK sample(s) which significantly affect the calculation of PK parameters. The PK population will be used for the primary PK analysis and other secondary PK endpoint analyses ( $T_{\text{max}}$ , $C_{\text{av}}$ , and CL/F).

The determination of PK population independent of the PK test results will be finalized prior to the releasing of the study database.

Protocol deviations independent of PK test results will be determined on an ongoing basis per data review. Any participant with major protocol deviations that affect PK assessment as determined by the study team will be excluded from the PK population. Major protocol deviations may include: Missing or incomplete dosing (the first dose of the study in TP1 cannot be missed, no more than 1 missed dose allowed per TP except Week 32 dose, no more than 2 missed doses allowed in TP1 through TP4 except Week 32 dose, participants can only miss or have an incomplete dose for either the first or second dose in TP4 (but not both), and the study doses on Weeks 26, 28, and 30 cannot be missed or incomplete). During the conduct of the study, it is possible that other deviations will be identified that can impact PK assessments, which can result in additional deviations to those noted above.

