### 9.3. Populations for Analysis

The PK Population is defined as all randomized participants who are dosed to initiate the Week 30 steady state PK profile, remain on background MTX with no major protocol deviations influencing the PK assessment, such as a missing dose (the first dose of the study in TP1 cannot be missed, no more than 1 missed dose allowed per TP except Week 32 dose, no more than 2 missed doses allowed in TP1 through TP4 except Week 32 dose, participants can only miss or have an incomplete dose for either the first or second dose in TP4 (but not both), and the study doses on Weeks 26, 28, and 30 cannot be missed or incomplete), and have at least 1 primary endpoint ( $AUC_{\tau}$  or  $C_{max}$ ). The last study dose in TP4 on week 32 after the PK assessments is not included in the definition of the population for analyses and can be missed or be incomplete. Subjects will be excluded from the PK population in case of missed PK sample(s) which significantly affect the calculation of PK parameters. The PK population will be used for the primary PK analysis and other secondary PK endpoint analyses ( $T_{max}$ ,  $C_{av}$ , and CL/F).

The Enrolled Population is defined as all participants who are enrolled in TP1. This population will be used for participant accountability in TP1.

The Safety Population for TP1 (Safety-TP1) is defined as all participants who are enrolled in TP1 and receive at least one dose of investigational product in TP1. This population will be used for the TP1 safety analyses.

The Intent-to-Treat Population (ITT-Randomized) is defined as all participants who are randomized to a study treatment group at Study Week 10. This population will be used for participant accountability during TP2 through TP4.

The Safety Population (Safety-Randomized) is defined as all participants who are randomized and receive at least one dose of investigational product following the randomization at Study Week 10. The Safety Population will be used for the safety analyses during TP2 through TP4, ADA and NAb analyses and the secondary PK endpoint ( $C_{trough}$ ).

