### **6.5. Baseline and Other Summaries and Analyses**

#### **6.5.1. Participant disposition**

Participant disposition will be summarized for enrolled population and ITT-Randomized population and will include the number and percentage of participants enrolled, randomized, treated, status, reason/description and other relevant data.

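### Removing one site from every analysis population, not only the PK set, leaves its participants out of the accountability tables and its serious events out of the planned safety summaries

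*SAP*

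**What the plan says.** SAP section 4 states that every subject at one site (identifier redacted) "will be excluded from all the analysis populations due to violation of GCP principles (i.e., suspected falsification of study records". The SAP's version history lists this as a change made in version 2.

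The table directly below that sentence defines the sets with no site exception:

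- Enrolled: "All participants who are enrolled in TP1. This population will be used for participant accountability in TP1".
- Safety-TP1: "All participants who are enrolled in TP1 and receive at least one dose of investigational product in TP1".
- ITT-Randomized: "All participants who are randomized to a study treatment group at Study Week 10", used for accountability from TP2 to TP4.
- Safety-Randomized: "All participants who are randomized and receive at least one dose of investigational product following the randomization at Study Week 10".

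Protocol section 9.3 has the same definitions, again without a site exception: "The Enrolled Population is defined as all participants who are enrolled in TP1", and "The Intent-to-Treat Population (ITT-Randomized) is defined as all participants who are randomized to a study treatment group at Study Week 10".

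The outputs follow these sets. In SAP 6.5.1, "Participant disposition will be summarized for enrolled population and ITT-Randomized population". Exposure (SAP 6.5.3) and the AE, SAE and laboratory summaries (SAP 6.6) use Safety-TP1 and Safety-Randomized.

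**The concern.** An accountability set exists to show what happened to everyone who entered or was randomised. Once randomised people are taken out of it, it no longer does so. The same rule takes the site out of the safety sets, and safety of switching is a secondary objective of the trial.

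The setting makes open accounting more important. The trial is open-label, has no data monitoring committee, and the sponsor reviews data as the trial proceeds (Protocol 9.5 and 9.5.1). A reader of the planned tables could not see how many people were removed, from which arm, or with what serious events. Suspicion that records were falsified is a reason to distrust the data. It does not show that nobody at the site was dosed or harmed.

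**Working it through.** The point rests mainly on setting the rule beside the definitions and outputs. The plan gives no figure for the site, so there is none to reproduce.

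**Step 1: reach of the rule.** It covers all analysis populations, so it applies to Enrolled, Safety-TP1, ITT-Randomized, Safety-Randomized and PK, and on its wording also to the period-specific safety sets in SAP 6.6.1.2.2.

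**Step 2: effect on each output.**

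| Output | Set used | Effect of the rule as written |
|---|---|---|
| Disposition, TP1 (SAP 6.5.1) | Enrolled | Count is below the number enrolled |
| Disposition, TP2 to TP4 (SAP 6.5.1) | ITT-Randomized | Count is below the number randomised |
| Exposure (SAP 6.5.3) | Safety-TP1, Safety-Randomized | Site's dosing absent |
| AE and SAE summaries (SAP 6.6.1) | Safety-TP1, Safety-Randomized | Site's events absent |
| Ctrough, ADA and NAb (SAP 6.2.1, 6.2.2) | Safety-Randomized | Site's samples absent |
| Cmax and AUCτ (SAP 6.1.1) | PK | Site absent; defensible |

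**Step 3: the accounting gap.** If N participants were randomised and k of them were at the site, the ITT-Randomized table shows N − k. By arm it shows N_s − k_s and N_ns − k_ns. The SAP plans no display of k, k_s or k_ns. Randomisation is described as stratified by three weight groups only (Protocol 4.1 and 6.3), so an even split between arms within a site cannot be assumed.

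**Step 4: is the gap filled elsewhere?** The SAP describes no count of those removed, no listing of their events and no safety summary with the site included. Protocol 9.4 says that the SAP will set out how spurious data are accounted for; the SAP gives the exclusion but not the accounting. For COVID-19 it does plan this kind of output: related deviations, discontinuations, AEs and SAEs are listed or summarised by arm (SAP 6.6.4).

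**Step 5: possible size.** Input from the documents: a planned maximum of about 420 enrolled (Protocol 4.1 and 9.2). Assumption: site size m of 10, 20 or 40, because the documents do not give it. Formula: share = m / 420.

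- 10 / 420 = 2.4%
- 20 / 420 = 4.8%
- 40 / 420 = 9.5%

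These are shares of planned enrolment. The actual numbers enrolled and randomised are not in the documents.

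**The case against.** The strongest reply has four parts.

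- **The exclusion is declared and permitted.** It stands directly above the definitions as a general exception, with its reason. Protocol section 9 lets the SAP modify the protocol's plans and asks for an amendment only for major changes to the primary endpoint definitions or their analyses. This stands: the rule is neither hidden nor barred. But permission to change a set does not supply the missing counts.
- **Nothing is lost.** A reader might infer that the site's serious events disappear or that no record is kept. The documents do not support that. SAEs in the active collection period go to sponsor safety within 24 hours (Protocol 8.3.1.1), population classifications are documented before database release (SAP 4), and records are kept for 15 years (Protocol 10.1.6). What is missing is a planned reported output.
- **Silence is not proof.** The SAP does not claim to list every output. Its disposition section allows for reasons and other relevant data, and one safety analysis is deferred to a supplemental specification (SAP 6.6.1.2.1). A site listing may therefore exist. Still, a disposition table built on a set without these participants cannot show their reason for leaving it.
- **The data may be false.** Dosing and AE records from the site may be unreliable, so even membership of a Safety set may not be verifiable. This is a good reason to keep the site out of the main safety summaries and to label anything shown as unverified. It is a weaker reason to leave these people out of the count of those enrolled and randomised.

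A reader might also infer that the exclusion undermines the primary PK comparison or was chosen with knowledge of results. The documents do not show this. The stated ground is site-wide and not arm-specific, population decisions are placed before database release, and no release date is given to set against the SAP date of 13 July 2021.

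**Conclusion.** The concern holds as a point about accountability and safety reporting. Applied as written, the rule produces disposition tables that do not match the numbers enrolled and randomised, does not show the number removed by arm, and leaves the site's deaths and SAEs out of every population-based safety output the SAP describes. It does not call into question the exclusion from the PK population.

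The size cannot be fixed from the documents. The range of 2.4% to 9.5% of planned enrolment rests wholly on assumed site sizes of 10 to 40. The mismatch itself does not depend on that range: it arises if the site had even one enrolled participant.

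**What to change.** Change SAP section 4 and the outputs that follow from it:

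1. Limit the exclusion to the PK population and the main safety, immunogenicity and Ctrough summaries.
2. Keep the site's participants in Enrolled and ITT-Randomized. Show 'site GCP exclusion' as a disposition reason, by arm for those randomised and under the Humira lead-in group for those who left during TP1.
3. List the site's reported deaths, SAEs, AESIs and discontinuations by arm, labelled unverified.
4. Repeat the overall AE/SAE summary with the site included, as a supplementary table.

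A repeat of the primary geometric mean ratio with the site included is not needed; a result that draws on suspected false concentrations would be hard to interpret either way.

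The cost is revised SAP wording, one disposition row, one listing and one supplementary table. The listing and the supplementary table would contain data of doubtful reliability and must say so. Demographics (SAP 6.5.2) also use Enrolled and ITT-Randomized, so the SAP should state whether the site is included there.
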